8.2. Secondary Efficacy Endpoints and Analyses

8.2.1. Proportion of participants with BTH

The proportion of participants who experience BTH through Day 351 will be summarized along with a 2-sided 95% exact CI using the Clopper-Pearson method.

The determination about whether a BTH has occurred will be reflected on the BTH form of the eCRF. In the event of a BTH outside the visit schedule, an unscheduled visit will occur, at which point all information pertaining to the BTH will be collected.

All data will be listed.

8.2.2. Hemolysis

Hemolysis is analyzed as directly measured as the percentage change in LDH from baseline.

The percentage change in LDH will be analyzed using a mixed model for repeated measures (MMRM) (Mallinckrodt, 2001; Mallinckrodt, 2004) with the fixed categorical effects of study visit, and the continuous fixed covariate of baseline LDH. Baseline is defined as the average of all assessments analyzed by the central laboratory prior to the first study drug administration. The Kenward-Roger approximation will be used to estimate denominator degrees of freedom. A p-value testing whether percent changes differ from 0 at each visit will be calculated.

Absolute LDH levels, and the change and percent change from baseline, will be summarized at all study visits up to Day 351.

This document is confidential

SAP Version: 2.0 09-Feb-2023

Controlled Document ID: 3903A.02, Effective Date 31-Aug-2020

The number (%) of participants achieving LDH levels at or below ULN (1.0 × ULN) and levels at or below 1.5 × ULN will be displayed.

Mean (±95% CI) of absolute LDH levels, and the change and percent change from baseline will be plotted over time.

All data will be listed.

8.2.3. Proportion of participants with transfusion

Proportion of participants receiving a transfusion from baseline to Day 351 will be summarized along with a 2-sided 95% exact CI using the Clopper-Pearson method. Number of transfusion episodes, number of units transfused will also be summarized for participants receiving transfusions.

Participants who withdraw from the study due to lack of efficacy during the Evaluation Period will be considered as non-responders and will be counted in the group receiving transfusion. For participants who withdraw from the study for any other reason during the Evaluation Period, their data up to the time of withdrawal will be used to assess the proportion of participants receiving a transfusion.

All data will be listed.

8.2.4. Proportion of participants with stabilized hemoglobin

Proportion of participants with stabilized hemoglobin in the absence of transfusion from baseline to Day 351 will be summarized along with a 2-sided 95% exact CI using the Clopper-Pearson method. Stabilized hemoglobin is defined as avoidance of a \geq 2 g/dL decrease in hemoglobin level from baseline in the absence of transfusion from baseline to Day 351.

Participants who withdraw from the study because of lack of efficacy during the Evaluation Period will be considered as non-responders and will be counted in the group who did not meet the stabilized hemoglobin definition. For participants who withdraw from the study for any other reason during the Evaluation Period, their data up to the time of withdrawal will be used to assess stabilized hemoglobin.

All data will be listed.

8.3. Exploratory Endpoints and Analyses

8.3.1. Patient-Reported PNH symptoms

For PRS, each participant will record the presence or absence of the following signs and symptoms of PNH at baseline, Day 183, and Day 351/ET: fatigue, chest pain, abdominal pain, dyspnea, dysphagia, headache, confusion, erectile dysfunction (if applicable), discoloration of urine, and discoloration of eyes.

PRS data will be summarized descriptively by visit for the FAS. The summaries will include the proportion of participants affected by PNH symptoms, the frequency and severity of those symptoms, and the level of distress the symptoms caused.

All data will be listed.

8.3.2. Healthcare Resource Utilization

For HRU, the Investigator or designee will record for each participant the number of clinic visits, emergency services utilized, hospitalization, missed work and also record the number of times the participant had darkened urine at baseline, Day 183, and Day 351/ET.

This document is confidential

SAP Version: 2.0 09-Feb-2023

Controlled Document ID: 3903A.02, Effective Date 31-Aug-2020

HRU data will be summarized descriptively by visit for the FAS. The summaries will include the proportion of participants who required healthcare resource utilization within a month before the specified study visit and the frequency of HRU.

All data will be listed.

9. Pharmacokinetics

All pharmacokinetic analyses will be conducted on the PK Analysis Set.

The non-compartmental analysis will be performed using appropriate software, ie, Phoenix™ WinNonlin® (Version 8.0 or higher, Certara Corporation) to report on the basis of this SAP.

9.1. Plasma PK Endpoint

PK Sampling Schedule

Blood samples for determination of serum ravulizumab concentrations will be collected before and after administration of study drug at the timepoints as specified in the schedule of assessments (see Section 1.3 of the protocol). The predose (within 0.5 hours prior to the start of infusion) PK sample may be drawn through the venous access created for the dose infusion, prior to administration of the dose. End-of-infusion (within 0.5 hours after the end of infusion) PK samples will be drawn from the participant's opposite, non-infused arm. In the event of BTH, a serum PK sample will be collected.

9.2. Presentation of Concentration Data

9.2.1. Handling of Missing Data

Missing concentration data for all participants who are administered study treatment will be considered as non-informative missing and will not be imputed. No concentration estimates will be provided for missing sample values.

9.2.2. Handling of the Difference between the Scheduled (Nominal Time) and the Actual Sampling Times (Actual Time)

For all sampling times, the actual sampling times relative to dosing are calculated as the difference between the actual clock time of sampling and the actual clock time of dosing. The actual postdose sampling times relative to dosing expressed in hours and rounded off to 3 decimal digits are used. The predose sampling time will be reported as 0 (0.000), regardless of the time difference between the predose sampling and dosing. Scheduled sampling times are presented in concentration tables. If the actual time of sampling is missing, the nominal time is used.

9.2.3. Listing and Presentation of Individual PK Data

- The sampling time of predose samples relative to dosing is treated as 0 for all sampling periods separately;
- All concentrations are presented in original units as reported by the bioanalytical laboratory (eg, ng/mL);
- All concentrations that are below the lower limit of quantification (BLQ) will be set to half the lower limit of quantification (0.5 ug/mL).
- Listing of PK sampling times including nominal and actual time elapsed from dose with the deviation from the nominal time and measured concentrations of the drug;
- No further imputation will be applied to any missing values.

This document is confidential

SAP Version: 2.0 09-Feb-2023

Controlled Document ID: 3903A.02, Effective Date 31-Aug-2020

Individual serum ravulizumab concentration data will be listed by participant, timepoint, and treatment (in relevant concentration units). Data will be presented by rounding off to 2 decimal digits. Individual serum concentrations versus time profiles for individual participants will be generated on linear and log-linear scales.

9.2.4. Summary of PK Concentrations

For PK concentration summary, the following rules apply:

- PK concentrations BLQ in predose samples and in samples taken before the time of the first quantifiable value are set to half the lower limit of quantification (0.5 ug/mL).
- The PK concentrations BLQ after quantifiable concentration are set to 0;
- The sampling time of predose samples relative to dosing will be treated as 0;
- Drug concentrations will be summarized by nominal timepoint;
- Descriptive statistics will be performed;
- No further imputation is applied to any missing values.

Ravulizumab concentrations will be summarized descriptively by visit and timepoint (in relevant concentration units) using descriptive statistics (n, number and percent of participants with BLQ, arithmetic mean, geometric mean, SD, arithmetic and geometric coefficient of variation (CV) %, minimum, median and maximum) presented according to the following reporting precision.

Variable	Summarized with:
Minimum, Maximum	3 significant digits or as needed based on actual measured values
Arithmetic Mean, Geometric Mean, Median	4 significant digits or as needed based on actual measured values
SD	5 significant digits or as needed based on actual measured values
CV%, and Geometric CV%	1 decimal place or as needed based on actual measured values

Mean (± SD) concentration-time profiles, on linear and log-linear scales versus nominal time will be generated.

9.3. PK Parameters Derivation

Only C_{trough}, C_{max}, accumulation ratio, and attainment of steady state for ravulizumab will be reported. No other PK parameters are possible to calculate due to limited sampling schedule.

9.3.1. PK Parameters Summarization

C_{max} and C_{trough} will be summarized descriptively using n, arithmetic mean, SD, CV%, minimum, median, maximum, geometric mean, and geometric CV%.

Accumulation ratio will be calculated for both C_{max} and C_{trough} following the first and last maintenance dose of ravulizumab.

This document is confidential

SAP Version: 2.0 09-Feb-2023

Controlled Document ID: 3903A.02, Effective Date 31-Aug-2020

Attainment of steady state will be calculated using the slope, corresponding 95% CI, and P-value of Ctrough values at Days 15, 71, 127, 183, 239, 295, and 351.

The model will be used to assess whether steady state was achieved for ravulizumab where sufficient data are available. Aggregate assessment of trough concentrations by repeated measures ANOVA will be used to evaluate attainment of steady state. The approach is based on the comparison of log-transformed trough concentration values to the mean of the results for all the succeeding doses up to Day 351.

Repeated measures analysis will be carried out on log-transformed trough levels (predose concentrations) for Days 15, 71, 127, 183, 239, 295, and 351.

The example SAS code will be:

PROC MIXED DATA=xx;

CLASS dose time patient id;

MODEL log(PK parameter) = treatment treatment*time / DDFM=KR;

REPEATED / TYPE=UN SUBJECT=patient_id(dose);

LSMEANS dose*time;

RUN;

The DDFM = KR (KenwardRoger) option performs the degrees-of-freedom calculations detailed by Kenward and Roger (1997). As recommended the denominator degrees of freedom for the fixed effects will be estimated as the most appropriate method in the mixed-model analysis.

Contrasts will be tested between a particular time point and the pooled mean over all remaining time points:

Day 15 / the average pre-dose Day 71 through Day 351

Day 71 / the average pre-dose Day 127 through Day 351

Day 127 / the average pre-dose Day 183 through Day 351

Day 183 / the average pre-dose Day 239 through Day 351

Day 239 / the average pre-dose Day 295 through Day 351

Day 239 / the average pre-dose Day 351

The first non-significant comparison will be concluded to be the day number (Day x) at which steady state concentrations are attained. The p-value for difference of Least Square Means (LSM), LSM Ratio, and the 95% confidence interval for the contrasts will be provided.

The precision for the descriptive statistics of PK parameters will follow the same as the aforementioned descriptive statistics of ravulizumab concentration (see Section 9.2.4).

This document is confidential

SAP Version: 2.0 09-Feb-2023

Controlled Document ID: 3903A.02, Effective Date 31-Aug-2020

10. Pharmacodynamics

Serum samples will be collected for free and total C5 analyses (before eculizumab dosing) during Screening on Day -57 and Day -29. During the evaluation period serum free and total C5 concentrations will be collected before and after administration of study drug at the timepoints specified in the schedule of assessments (see Section 1.3 of the Protocol). In the event of BTH, a serum sample for PD analysis will be collected. In the event of an unscheduled visit, a PD blood sample will be collected as soon as possible.

Pharmacodynamic analyses will be conducted PD set.

The PD effects of ravulizumab administered IV will be evaluated by assessing the absolute values, and changes and percentage changes from baseline in total and free C5 serum concentrations over time, as appropriate. In addition, mean free C5 concentrations, and number and percentage of participants with free C5 concentrations $\geq 0.5 \, \mu \text{g/mL}$ will be presented over time.

Mean (95% CI) for absolute values, change and percentage change from baseline over time will be presented graphically for free and total C5. For free C5 boxplots will also be presented over time.

A by-participant listing will also be produced.

SAP Version: 2.0 09-Feb-2023

Controlled Document ID: 3903A.02, Effective Date 31-Aug-2020

11. Safety

The population used for safety analyses will be the Safety Set. Safety will be assessed on the basis of AE reports, clinical laboratory data, electrocardiogram (ECG) parameters, physical examinations, vital signs, and immunogenicity data, using descriptive statistics.

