### Table 2: Schedule of Study Visits and Assessments: Confirmation Visit Through Follow-up

Period	Confirmation Visit			Eval	uation	Period			Unscheduled Visits	Follow- up call	Notes
Study Day	1	15	71	127	183	239	295	351/ ET	NA	407	
Window (day)	NA	± 2	±7	± 7	± 7	± 7	± 7	± 7		± 7	
PRS and HRU	X				X			X			Questionnaires at the confirmation visit administered prior to first dosing of Ravulizumab. PRS completed by the participant Refer to Section 8.10 for details
Record transfusions and transfusion parameters	Х	X	Х	Х	Х	Х	Х	Х	X		Transfusions given during and between visits will be recorded
PNH symptomatology	Х	X	X	X	X	X	X	X	Х		Investigator assessed and reported Refer to Section 8.1.3 for details
PK/PD sampling	Х	X	X	X	X			X	Х		Refer to Section 8.5 and Section 8.6 for details
Immunogenicity (ADA)	Х		X		X			X	Х		Samples will be collected predose
Review safety card	Х	Х	X	X	Х	X	X	Х	Х		
BTH				If a suspected event of BTH occurs, LDH, PK, and PD samples will be collected and analyzed . If the suspected event of BTH does not occur at a scheduled visit, an unscheduled visit should occur for evaluation of the participant and collection of the required LDH, PK, and PD samples.							
Concomitant medications				<del>(</del>	-Monito	r continu	ously→			•	
Adverse events				+	-Monito	r continu	ously→				

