### Table 2: Schedule of Study Visits and Assessments: Confirmation Visit Through Follow-up

Period	Confirmation Visit		Evaluation Period			Unscheduled Follow- Visits up call	Notes				
Study Day	1	15	71	127	183	239	295	351/ ET	NA	407	
Window (day)	NA	± 2	± 7	± 7	± 7	± 7	± 7	± 7		± 7	
Ravulizumab administration	X	X	X	X	x	x	X		X		The dose of ravulizumab is based on the participant's last recorded study visit body weight as per approved dose regimen. Refer to Section 6.1.1 At the Investigator's discretion and in accordance with the local regulations, ravulizumab may be administered at the patient's home or at a medical facility close to the patient's home by a qualified healthcare personnel (see Section 8.11).

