#### Table 2: Schedule of Study Visits and Assessments: Confirmation Visit Through Follow-up

Abbreviations: ADA = antidrug antibody; AE = adverse event; BTH = breakthrough hemolysis; C5 = complement component C5; ECG = electrocardiogram; ET = early termination; LDH = lactate dehydrogenase; LDH-PCHG = lactate dehydrogenase percent change; NA = not applicable; PD = pharmacodynamic; PK = pharmacokinetic; RBC = red blood cell; SAE = serious adverse event; WBC = white blood cell.

	Starting Visit	Example Visit	EOS/ET	Unscheduled visit	Follow- up call	Notes
Study Day	q6w Day 1	q6w Day 43	Day XX	NA	EOS/ET + 56 days	All subsequent q6w visits up to EOS/ET to follow the assessments shown in the example visit
Window (day)	NA	± 7	± 7		± 7	
Physical examination			Х			
Abbreviated physical examination	Х	Х		Х		Refer to Section 8.2.1 for details
Weight	Х	Х	Х	Х		
Serum or urine pregnancy test	Х	Х	X	Х		Refer to Section 8.3.5 for details
Chemistry including LDH	Х	X	X	Х		Sample to be collected within 24 hours of or immediately prior to a scheduled dose of study drug (trough) and not from a heparinized line.
Hematology including free hemoglobin and coagulation	Х	X	X	X		Blood will be collected predose on dosing days and not from a heparinized line.
Urinalysis and urine chemistry	Х	Х	Х	Х		Urine will be collected predose on dosing days.
Safety 12-lead ECG	Х		Х			Refer to Section 8.2.3 for details
Vital signs	Х	Х	Х	Х	Will be measured after the participant has been resting for 5 minutes. Refer to Section 8.2.2 for details	
PNH clone size	Х	X	X			WBC (granulocyte and monocyte) and RBC clone size measured by high-sensitivity flow cytometry at Day 1; RBC clone size only at Day 127 and Day 351/ET
Record transfusions and transfusion parameters	Х	Х	X	X		Transfusions given during and between visits will be recorded
PNH symptomatology	Х	X	X	X		Investigator assessed and reported. Refer to Section 8.1.3 for details
PK/PD sampling	Х	Х	Х	Х		Refer to Section 8.5 and Section 8.6 for details

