# 4. STUDY DESIGN

### 4.1. **Overall Design**

This is a Phase 4, multicenter, single-arm, open-label study to evaluate safety and efficacy of ravulizumab in adult participants with PNH who switch from eculizumab 1200 mg q2w to ravulizumab.

The study will consist of a Screening Period of approximately 3 months and a Treatment Period of 351 days.

Approximately 20 participants will be enrolled. Eligible participants will be administered eculizumab 1200 mg q2w optionally at home at the discretion of the Investigator, and preference of the patient (see Section 8) during the Screening Period followed by a loading dose of ravulizumab on Day 1, and maintenance treatment with ravulizumab on Day 15 and q8w thereafter until Day 351. Ravulizumab loading and maintenance doses will be based on the participant's body weight measured at the prior visit, per approved dosing regimen. Ravulizumab dosing will be administered in the clinic by a trained member of the site study team; patients may have the option to receive study drug remotely at a medical facility that is located near the patient's home or at the patient's home through a qualified healthcare personnel (see Section 8.11). The schedule of study visits and assessments is shown in Section 1.3.

An interim analysis will be performed on Day 183.

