### 6.6.2. Permitted Change in Dosing Interval

If a participant experiences a free C5-related BTH during maintenance treatment with ravulizumab, shortening the dosing interval to every 6 weeks (q6w) is permitted at the discretion of the Investigator after discussion with Alexion's Medical Monitor. For these participants, the assessments performed at the first q6w visit would be those indicated in the SoA (Section 1.3). Subsequent q6w visit assessments would continue to be aligned to the example visit illustrated in Table 3, with the EOS/ET visit being on/after Day 351. Between the SoA-specified visits occurring at 6-week dosing frequency and the EOS/ET visit, any additional visits are to be classified as unscheduled visits and would follow the study procedures for unscheduled visits (Table 3).

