## 8.5.2. Sample Collection during Confirmation Visit Through Follow-up

Blood samples for determination of serum drug concentrations and PD assessments will be collected before and after administration of study drug at the time points as specified in the SoA (Section 1.3). The predose (within 0.5 hours prior to the start of infusion) PK/PD sample may be drawn through the venous access created for the dose infusion, prior to administration of the dose. End-of-infusion (within 0.5 hours after the end of infusion) PK/PD samples will be drawn from the participant's opposite, non-infused arm. All collection times will be recorded in the eCRF. In the event of BTH, a serum PK/PD sample will be collected.

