4.5. PK/PD Endpoints

- Serum ravulizumab concentration over time
- Change in serum free and total C5 concentrations over time

This document is confidential.

SAP Version: 2.0 09-Feb-2023

Controlled Document ID: 3903A.02, Effective Date 31-Aug-2020

5. Analysis Sets

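### All six steady-state contrasts in SAP 9.3.1 use trough Days 239 and/or 295, which Protocol Table 2 does not sample, so none is estimable as written from the scheduled q8w samples

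*SAP*

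**What the plan says.** - **Analysis.** SAP 9.3 reports four PK results: trough, peak, accumulation ratio and attainment of steady state. SAP 9.3.1 fits a repeated-measures model to "log-transformed trough levels (predose concentrations) for Days 15, 71, 127, 183, 239, 295, and 351" and a slope over the same seven days. Six contrasts follow, each setting one day against the mean of all later days. The earliest day whose contrast is not significant is declared the day of steady state. The section says the model is used when the data suffice, but it names no reduced set of days or contrasts.
- **Sampling.** SAP 9.1 takes its PK times from Protocol Section 1.3 and adds none. SAP 9.2.1 imputes no missing concentration. In Protocol Table 2 the row "PK/PD sampling" is marked at Days 1, 15, 71, 127, 183, 351/ET and unscheduled visits, and is blank at Days 239 and 295.
- **Dosing.** In Table 2 the row "Ravulizumab administration" is marked at Days 1, 15, 71, 127, 183, 239 and 295 and at unscheduled visits. Protocol 4.1 instead describes "maintenance treatment with ravulizumab on Day 15 and q8w thereafter until Day 351".
- **Interval change.** After a free C5-related breakthrough hemolysis, "shortening the dosing interval to every 6 weeks (q6w) is permitted at the discretion of the Investigator" (Protocol 6.6.2). Protocol Table 3 marks PK sampling for these participants at each visit: "All subsequent q6w visits up to EOS/ET to follow the assessments shown in the example visit".
- **Accumulation ratio.** SAP 9.3.1 computes it for peak and trough from the first and last maintenance doses. Protocol 8.5.2 obtains peaks from "End-of-infusion (within 0.5 hours after the end of infusion) PK/PD samples".
- **Endpoint status.** The PK endpoint in SAP 4.5 is "Serum ravulizumab concentration over time". The day of steady state is not listed there.

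**The concern.** The SAP asks for troughs on two dosing days when no PK sample is scheduled, and it builds every decision contrast on at least one of them. The steady-state day is read off the sequence of contrasts, so the result depends on which contrasts exist and how precise each one is. If none can be computed from the scheduled data, someone must choose replacement contrasts at analysis, after seeing the concentrations. If a few participants happen to have values in those windows, the software may return estimates that depend on those few people. The accumulation ratio for peak concentration has a similar gap at the last dose.

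**Working it through.** **Inputs.** Seven trough days and six contrasts (SAP 9.3.1); sampled and dosed days (Protocol Table 2); analysis windows (SAP 6.4). No sample-size or power figure depends on this point.

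**Is the blank real?** The rows for patient-reported symptoms with resource utilization and for antidrug antibodies are also blank at Days 239 and 295. Rows done at every visit, such as transfusions, are marked there. So the gap is in the schedule and is not a table-reading artefact. SAP Section 14 lists no added sampling days.

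**Estimability.** With cell means by day, each scheduled observation informs one of Days 15, 71, 127, 183 or 351. A contrast is estimable only if its coefficients on Days 239 and 295 are both zero.

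| Contrast | Day tested | Days averaged | Coefficient, 239 | Coefficient, 295 | Share of average unsampled | Estimable |
|---|---|---|---|---|---|---|
| 1 | 15 | 71, 127, 183, 239, 295, 351 | −1/6 | −1/6 | 2/6 = 33% | No |
| 2 | 71 | 127, 183, 239, 295, 351 | −1/5 | −1/5 | 2/5 = 40% | No |
| 3 | 127 | 183, 239, 295, 351 | −1/4 | −1/4 | 2/4 = 50% | No |
| 4 | 183 | 239, 295, 351 | −1/3 | −1/3 | 2/3 = 67% | No |
| 5 | 239 | 295, 351 | +1 | −1/2 | 1/2 = 50% | No |
| 6 | 239 | 351 | +1 | 0 | 0/1 = 0% | No (tested day unsampled) |

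A numerical rank check gives the same answer with and without an intercept: 0 of 6. By the pattern, contrast 6 was probably meant to test Day 295, but that day is unsampled too. If the averages are limited to sampled days, contrasts 1 to 4 become estimable (4 of 6), and 5 and 6 remain impossible.

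**Can other samples fill the gap?** The windows are Days 211–266 (Day 239) and 267–322 (Day 295). The latest on-schedule Day 183 sample is 183 + 7 = 190, below 211. The earliest on-schedule Day 351 sample is 351 − 7 = 344, above 322. So no on-schedule q8w sample reaches either window. Values could come only from q6w visits, or from unscheduled, early-termination or off-window visits. For example, q6w dosing started at Day 127 gives visits at 127 + 42 = 169, then 211, 253 and 295. Days 211 and 253 map to Day 239, and Day 295 maps to Day 295.

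**Accumulation ratio.** Under Table 2 the first maintenance dose is Day 15 and the last is Day 295.
- Peak: Day 15 is sampled and Day 295 is not, so the ratio has no scheduled numerator.
- Trough: the Day 15 dose is followed by the Day 71 sample, and the Day 295 dose by the Day 351 sample. Both exist.
- If Protocol 4.1 means a dose on Day 351, the trough after it has no sample, because Day 407 is a call with no PK mark.

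**Example code.** LSMEANS requests a dose-by-time effect, but MODEL contains only treatment and treatment-by-time. The requested effect is not in the model.

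**The case against.** **The SAP can be read as averaging whatever was sampled.** It imputes nothing and limits the model to cases with enough data. For contrasts 1 to 4 the tested day is sampled, and averaging the sampled later days yields four workable contrasts. This stands as a description of what can be done. But the SAP defines the comparator as all later time points and states no such restriction, and contrasts 5 and 6 fail on either reading.

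**The Day 351 sample is not strictly predose under Table 2,** because no dose is marked that day. This stands to the extent that the SAP should say how the sample counts. It falls at the end of the interval after the Day 295 dose, so it can serve as that dose's trough.

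**The documents point both ways on the last dose.** Tables 2 and 3 mark no scheduled dose at the final visit, and SAP 7.6 counts maintenance doses before Day 351. SAP 3.1, however, places the follow-up call about two months after the last dose. With the call at Day 407, 407 − 351 = 56 days and 407 − 295 = 112 days. The passages need reconciling, and this review does not say which is right.

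**Three stronger readings are tempting and are not supported.**
- A reader might infer that steady state cannot be assessed at all. The slope and a repeated-measures model can still be fitted on the five sampled days.
- A reader might infer a predictable error in the steady-state day. The documents give neither the number of q6w switchers nor how their troughs differ. The planned unstructured covariance could not be estimated reliably from one or two participants. No size or direction can be given.
- A reader might infer that post-switch troughs must leave the main model. SAP 6.4 already has a rule for q6w records, and removing them would be an exclusion that depends on outcome. The estimability error does not require it.

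**Conclusion.** SAP 9.3.1 is wrong as written. Two of its seven trough days have no scheduled PK sample, and 0 of 6 contrasts are estimable from the scheduled q8w samples. Contrasts 1 to 4 need redefinition, and contrasts 5 and 6 cannot be rescued. Any contrast made estimable by stray values would rest on a few selected participants. The missing numerator of the Cmax accumulation ratio is conditional on Table 2's last dose being Day 295.

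The counts rest only on the Table 2 schedule, the SAP's stated definition of the contrasts and the SAP 6.4 windows. No modelling assumption is involved.

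Severity is minor. Primary, secondary and safety endpoints are unaffected, as are the concentration summaries at sampled visits, and the day of steady state is not a listed endpoint.

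**What to change.** 1. In SAP 9.3.1, limit the trough days to 15, 71, 127, 183 and 351. State that, under Table 2, the Day 351 sample counts as the end-of-interval trough of the Day 295 dose.
2. Replace the six contrasts with four: 15 vs mean(71, 127, 183, 351); 71 vs mean(127, 183, 351); 127 vs mean(183, 351); 183 vs 351. Drop contrasts 5 and 6.
3. Make the example code consistent: time as the fixed effect, and LSMEANS matching MODEL.
4. Reconcile Protocol 4.1 with Table 2 on which dose is last. Then define both accumulation ratios on doses with scheduled samples. Under Table 2 these are Cmax Day 183 vs Day 15 and Ctrough Day 351 vs Day 71.
5. Keep the SAP 6.4 rule for q6w records. A q8w-only analysis may be added as a sensitivity analysis.

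**Cost.** SAP text and code plus one protocol clarification, with no new samples. The analysis has five trough days instead of seven and four contrasts instead of six. Only Day 351 informs troughs after Day 183, and under Table 2 the Cmax ratio ends at Day 183.
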